## **8.0 DATA MANAGEMENT AND DATA SAFETY MONITORING PLAN**

The number of IL-2 doses administered, severe adverse events, including their relatedness to HCQ (definitely, probably, possibly or unlikely), clinical response (Section 10.3), date of progression and date of death will be forwarded immediately to the Data Coordinating Center at UPCI for monthly presentation to the CWG and the UPCI Multi-Center DSMC. The UPCI IMCPL will report to the DCC on samples received on a monthly basis. Biomarker and laboratory data that will be evaluated at the end of the trial need only be reported to the DCC when the trial is closed to accrual, but more timely reporting is advisable so that missing and questionable data can be resolved prior to final data analysis. The DCC will use the UPCI Clinical Trials Management Application to store and manage all demographic, clinical, laboratory and biomarker data required to achieve the Specific Aims.

## 9.0 EVALUATION AND MANAGEMENT OF TOXICITY (DOSE MODIFICATION)

### 9.1 General

Investigator/Sub-investigators, regulatory, CRS management, clinical research coordinators, clinical research associates, data managers, and clinic staff meet regularly in disease center Data Safety Monitoring Boards (DSMB) to review and discuss study data to include, but not limited to, the following:

- serious adverse events
- subject safety issues
- recruitment issues
- accrual
- protocol deviations
- unanticipated problems
- breaches of confidentiality

All toxicities encountered during the study will be evaluated on an ongoing basis according to the NCI Common Toxicity Criteria version 4.0 and recorded prior to each course of the investigational therapy. Any modifications necessary to ensure subject safety and decisions to continue, or close the trial to accrual are also discussed during these meetings. All study data reviewed and discussed during these meetings will be kept confidential. These reviews are summarized by each respective disease center and submitted to the University of Pittsburgh Cancer Institute's Data and Safety Monitoring Committee (UPCI DSMC) for their monthly review of all disease centers' studies. The UPCI DSMC will provide oversight for this study. At the time of renewal a summary of all serious adverse events and modifications will also be reported to the UPCI DSMC.

Any modifications necessary to ensure patient safety will be submitted to the IRB prior to implementation. The IRB will be notified of any change in the risk/benefit ratio which would affect whether the study should continue. All protocol deviations or breaches of confidentiality will be reported to the IRB according to IRB guidelines. If any literature becomes available which suggests that conducting this trial is no longer ethical the study will be terminated and the IRB will be notified of the new findings in the form of an Unanticipated Problem submission. All study treatment associated adverse events that are serious, at least possibly related and unexpected will be reported to the IRB. DSMC reports and approval will be submitted to the IRB at the time of renewal.

All records related to this research study will be stored in a locked environment. Only the researchers affiliated with the research study and their staff will have access to the research records.

Safety data for each patient at the end of each cycle of IL-2 will be provided by all sites to the PI at UPCI.

Patients with life-threatening or persistent, severe toxic reactions to IL-2 will receive no further treatment with this agent. Specific toxicities, which require special consideration, are discussed below. Previously unknown or severe toxicities will be reported to the PI as Adverse Drug Reactions. They will also be reported to the FDA on FDA Form 3500A Medwatch report. A courtesy copy of these reports will also be forwarded to Prometheus Drug Safety Department. See section 12.0.

## 9.2 Dose Modification for Toxicity: HD IL-2 and Hydroxychloroquine

Modification of the treatment protocol will occur by withholding doses of IL-2 rather than continuing therapy at a reduced dose. The only dose modification for patients of Hydroxychloroquine will be for those individuals deemed by the treating investigator as ‘likely’ due to hydroxychloroquine or the combination and not to IL-2 alone based on their experience and dose reduction as shown in **Table 5**. Missed doses of IL-2 will not be made up. Dose of IL-2 will be withheld for:

**9.2.1 Hypotension** refractory to fluids and pressors or requiring unacceptably high pressor doses (those associated with individual decrease in extremity perfusion). We will use vasopressors judiciously where necessary to support patients with limiting kidney/other organ perfusion. Requirement for vasopressors will be a relative indication for concluding a cycle (see 10.4.2.3 below).

**9.2.2 Anuria** for >24 hours and unresponsive to fluid replacement

**9.2.3 Respiratory distress** requiring oxygen >4 liters to maintain O2 saturation >95%.

**9.2.4 Confusion** (mental status changes can progress to paranoia despite discontinuation of IL-2; it is imperative that the IL-2 be stopped at any sign of persistent confusion or disorientation).

**9.2.5 Sustained ventricular tachycardia** or any sign or symptom of myocardial ischemia or myocarditis. Patients experiencing sustained ventricular tachycardia or myocardial ischemia should not receive further treatment with IL-2

**9.2.6 Metabolic acidosis** with HCO3 < 18, despite attempts to correct with IV HCO3.

**9.2.7 Atrial fibrillation or myocarditis.**

**9.2.8 Documented systemic infection.**

**9.2.9 Management of Nausea and Vomiting.** The frequency of nausea and vomiting with interleukin 2 administration falls within a broad category of moderate emetic risk (NCCN Practice Guidelines, 2010). It may be enhanced by HCQ. Patients with nausea and vomiting will be given 8 mg bid of ondansetron (a 5-HT3 receptor antagonist). For nausea and vomiting that is not controlled with regimen of ondansetron a general principle (NCCN Practice Guidelines, 2010) is to add one agent from a different drug class to the current regimen 5-HT3 and NK1 receptor antagonists are very safe drugs that are standards of care in this area. Although not well studied, by carefully monitoring NV and using appropriate treatments patients might have better nutrition and maintenance of body weight. Records of antiemetics given routinely or as part of symptom management will be recorded.

**or Any other serious toxicity** that is not controlled at time of next dose.

## 9.3 Specific IL-2 Toxicity Management

Several treatment-related toxicities have been uniquely associated with the administration of high-dose IL-2. Antihypertensive medication should be stopped prior to IL-2 therapy.

Recommendations for management of the more significant toxicities typically seen with high-dose bolus IL-2 are as follows (the following are only optional guidelines for toxicity management):

**9.3.1 Fluid Replacement.** Excessive fluid replacement will increase the patient's likelihood of developing pulmonary edema. It is suggested that when intravenous access has been established; begin administration of normal saline at 75cc/hour IV. Once patients have gained greater than 15% of baseline weight, elective discontinuation of IL-2 is recommended. Diuretics should not be given unless severe symptomatic fluid retention develops and blood pressure is adequate.

**9.3.2 Hypotension.** Administration of high dose IL-2 leads to decreased peripheral vascular resistance and consequent hypotension. In order to manage this toxicity, the physician may utilize the following guidelines:

1. Monitor patients in a setting capable of providing level high intensity care.
2. Prior to starting IL-2 therapy determine a minimum tolerated blood pressure (MTBP). For patients under age 40 and with no prior history of ischemic or valvular heart disease, the MTBP can be a systolic blood pressure (SBP) of 80 mmHg, while the MTBP for all other patients should be a SBP of 85-90 mmHg based on perceived risk of cardiac toxicity.
3. When a patient's systolic BP falls below the MTBP, suggested therapy may involve (in the following order):
  - a. Begin fluid boluses (250cc normal saline IV over 15 min. may repeat x 2) until SBP is > MTBP.
  - b. Should fluid boluses fail make the SBP>MTBP, vasopressor support such as phenylephrine could also be instituted (.1-2 ug/kg/min) to maintain SBP.
  - c. If blood pressure cannot be maintained on phenylephrine alone, or if unacceptable tachycardia develops, treatment with dopamine (1-6 ug/kg/min) should be added to sustain blood pressure.

**9.3.3 Management of Arrhythmias/Myocarditis.** If significant arrhythmias occur at any stage in the patient's treatment (whether on pressor agents or not), the possibility of myocardial ischemia/infarction must be excluded by both EKG and cardiac enzyme assessment. Patients who develop atrial fibrillation should have IL-2 doses held. Therapy may resume when the patient converts to normal sinus rhythm and is hemodynamically stable. If a significant supraventricular arrhythmia occurs while a patient is on dopamine therapy; neosynepherine should also be substituted for dopamine as initial blood pressure

support. Patients experiencing sustained ventricular tachycardia or documented myocardial ischemic episodes during therapy should not receive further treatment with IL-2. Patients with myocarditis may resume treatment in subsequent courses if CPK returns to normal. A cardiac ECHO documenting normal cardiac function should be performed prior to restarting therapy.

**9.3.4 Management of Neurotoxicity.** Doses are held rather than reduced for neurotoxicity. If Grade 4 neuro-cortical toxicity is encountered and is not reversible within 48 hours, no further treatment should be given and the patient should be removed from the study. If Grade 4 toxicity is reversible to Grade 1 within 48 hours, future treatment may be considered (in subsequent courses) if the patients shows any evidence of tumor regression and as discussed with the patient.

**9.3.5 Metabolic Acidosis.** In the course of IL-2 therapy, when a patient's  $\text{HCO}_3$  falls to below 20,  $\text{NaHCO}_3$  should be added to the maintenance IV infusion. Should the  $\text{HCO}_3$  level fall below 18, IL-2 therapy should be held, and bolus infusions of  $\text{NaHCO}_3$  should be instituted. IL-2 therapy may resume if repeat  $\text{HCO}_3 > 18$ . Sodium acetate may be substituted for  $\text{NaHCO}_3$  per institutional policy.

**9.3.6 Low Urine Output.** Fluid boluses and 'renal' dose dopamine may be administered. Weight gains/edema may serve as a basis for holding doses.

**9.3.7 Other Toxicities.** Increases in the serum creatinine to 2.0-3.5 mg/dl and total bilirubin to 3.0-10.0 mg/dl are common and reversible upon cessation of treatment. Doses of IL-2 have not generally been withheld for renal and hepatic dysfunction alone. Although toxicity may become severe, recovery usually occurs following cessation of IL-2 and vigorous supportive care is warranted.

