## **9.5 Toxicity Criteria for Discontinuing Treatment**

Patients will not be considered for further therapy if the following toxicities are encountered:

**9.5.1** Pulmonary toxicity requiring endotracheal intubation

**9.5.2** Renal dysfunction requiring dialysis

**9.5.3** Grade 4 cardiac dysrhythmia or Grade 2 or 3 dysrhythmia not easily controlled with medical management.

**9.5.4** Myocardial ischemia (Grade 3 or 4) or infarction or symptomatic myocarditis (note:

asymptomatic CPK or CPK-MB band elevations without EKG changes are not a contraindication to further treatment).

- 9.5.5** Coma
- 9.5.6** Life-threatening sepsis
- 9.5.7** Pericardial tamponade
- 9.5.8** Bowel ischemia or perforation
- 9.5.9** Grade 4 hypertension or reversible posterior leukoencephalopathy syndrome (RPLS)
- 9.5.10** Grade > 2 pulmonary or CNS hemorrhage
- 9.5.11** Grade 4 hypertension or hemorrhage, symptomatic grade 4 venous thromboembolic event, nephrotic syndrome
- 9.5.12** Any grade arterial thromboembolic event
- 9.5.13** Grade 4 congestive heart failure
- 9.5.14** Wound dehiscence requiring medical or surgical intervention
- 9.5.15** Inability of subject to comply with study requirements
- 9.5.16** Any other severe or life-threatening toxicity which, in the opinion of the investigator, would preclude further treatment with these agents, or has not resolved substantially to an acceptable level as determined by the local PI.

Patients who have an ongoing Grade 4 or serious adverse event at the time of discontinuation from study treatment will continue to be followed until resolution of the event or until the event is considered irreversible (see Section 7.1.3).

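### Sections 9.3.3 and 9.5.4 contradict each other on retreatment after symptomatic myocarditis, and the ischemia threshold in 9.5.4 differs from that in 9.2.5 and 9.3.3

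*Combined protocol and SAP*

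**What the plan says.** Four places in the combined protocol and SAP bear on retreatment after these cardiac events.

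- **Section 9.2** opens with "Dose of IL-2 will be withheld for" and lists triggers. Item 9.2.5 includes "any sign or symptom of myocardial ischemia or myocarditis", and 9.2.7 repeats "Atrial fibrillation or myocarditis". These entries withhold doses. Item 9.2.5 then adds a permanent stop: "Patients experiencing sustained ventricular tachycardia or myocardial ischemia should not receive further treatment with IL-2". Myocarditis is not named in that sentence.
- **Section 9.3** introduces its recommendations by saying that "the following are only optional guidelines for toxicity management". Within it, 9.3.3 repeats the IL-2 stop for documented ischemic episodes, again without a grade. On myocarditis it says "Patients with myocarditis may resume treatment in subsequent courses if CPK returns to normal", and it asks for an ECHO showing normal function before restart.
- **Section 9.5** opens with "Patients will not be considered for further therapy if the following toxicities are encountered". Item 9.5.4 reads "Myocardial ischemia (Grade 3 or 4) or infarction or symptomatic myocarditis", with a note that asymptomatic CPK or CPK-MB rises without EKG changes do not bar further treatment.
- **Section 6.4.2** allows up to three courses unless a listed criterion applies. For treatment-related toxicity it points to Section 9.5 and mentions neither 9.2 nor 9.3.

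**The concern.** An investigator deciding whether a patient may have another IL-2 course after a cardiac event should find one answer. For symptomatic myocarditis the answer depends on the section opened: 9.3.3 offers a conditional route back to treatment, and 9.5.4 closes it. For ischemia, the section that the duration-of-therapy text cites is narrower than the two sections it does not cite.

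What is at stake is patient safety and consistency between sites in a multi-center study. Two investigators could handle the same symptomatic myocarditis differently, and each could cite the protocol. The count of patients stopped for toxicity under 9.5 would then depend partly on which section a site followed.

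**Working it through.** No arithmetic applies and the plan states no figure on this point. The check sets the sections side by side for each event.

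| Event | 9.2.5 / 9.2.7 | 9.3.3 (labelled optional) | 9.5.4 (cited by 6.4.2) | Result |
|---|---|---|---|---|
| Symptomatic myocarditis | Withhold dose; no retreatment rule | May resume in a later course if CPK and ECHO are normal | No further therapy | Direct contradiction between 9.3.3 and 9.5.4 |
| Asymptomatic myocarditis | Withhold dose; no retreatment rule | May resume on the same conditions | Not listed as a stop | No opposite rules |
| Ischemia, Grade 1-2 | No further IL-2 | No further IL-2 after a documented episode | Not listed | Thresholds differ; no express permission to retreat |
| Ischemia, Grade 3-4 | No further IL-2 | No further IL-2 after a documented episode | No further therapy | No conflict over IL-2 |

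**Myocarditis.** The contradiction lies between 9.3.3 and 9.5.4 only. Items 9.2.5 and 9.2.7 hold doses and set no rule on later courses. It is confined to symptomatic cases because 9.5.4 stops therapy only for those. In practice it affects a patient with symptomatic myocarditis whose CPK and ECHO return to normal and who otherwise qualifies for a further course. For asymptomatic cases there is a smaller looseness: 9.3.3 makes a normal CPK a condition, while the 9.5.4 note says an asymptomatic CPK rise without EKG changes is no bar. The note concerns an enzyme rise rather than diagnosed myocarditis, so the two are not opposed.

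**Ischemia.** Two sections end IL-2 with no grade limit and the third names Grade 3 or 4. Retreatment after Grade 1-2 ischemia could be reached only by inference: 6.4.2 lets treatment continue until a listed criterion applies, its toxicity criterion refers to 9.5, and 9.5.4 omits Grade 1-2. Even then, the investigator-judgment provisions in 6.4.2 and 9.5.16 could stop treatment.

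**Scope of the stop.** The ischemia sentences in 9.2.5 and 9.3.3 name IL-2 alone. The opening of 9.5 speaks of therapy in general, and 9.5.16 refers to the agents in the plural. Section 9.5 may therefore be a second tier that ends both drugs, but nothing says so.

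**The case against.** The strongest defense is that the sections can be read together. Section 9.3 is optional and its myocarditis sentence is permissive; 9.5 is worded as mandatory, is more specific about symptoms, and is the list that 6.4.2 cites. On that reading, 9.3.3 naturally covers asymptomatic myocarditis only. For ischemia, an investigator who applies every section stops IL-2 at any grade, and 9.5.4 adds a stop of all therapy at Grade 3 or 4.

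Much of this stands. The optional label and the 6.4.2 link weaken the permission in 9.3.3. They do not remove it, because an optional guideline still offers an action that 9.5.4 forbids. Nor can all of 9.3.3 be treated as discretionary, since its ischemia sentence largely repeats the stop in 9.2.5. The harmonized reading is possible but written nowhere.

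Three stronger readings are tempting, and the documents do not support them:

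- **Opposite rules for lower-grade ischemia.** A reader might infer that Grade 1-2 ischemia may either end IL-2 or be followed by another course. Two sections bar IL-2 and the third is silent, so no retreatment is expressly allowed.
- **A link to the dose revision.** Section 2.18 reports pronounced hypotension and tachycardia in two of 13 patients at 1200 mg hydroxychloroquine. It reports no myocarditis or ischemia, so the connection is by organ system only.
- **An effect on the complete response count.** Access to later courses could in principle matter, but the documents give no event frequency from which to size it. Section 11.0 keeps eligible patients with at least one week of IL-2 in the main response analysis, so stopping after that point does not change the denominator.

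**Conclusion.** The concern holds in two limited parts. First, 9.3.3 and 9.5.4 contradict each other on retreatment after symptomatic myocarditis, and the optional label on 9.3 does not say which governs. Second, 9.5.4 sets a different ischemia threshold from 9.2.5 and 9.3.3, and the documents do not say whether 9.5 is a separate tier covering all study therapy.

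No numerical size can be given, because no frequency is stated for either event. The number of patients affected may be small, but each case would be a safety decision on which the protocol gives no single answer. The conclusion assumes that the word myocarditis in 9.3.3, which carries no qualifier, includes symptomatic cases. If the sponsor meant asymptomatic cases only, the contradiction disappears once the text says so. This review takes no view on which clinical rule is right.

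**What to change.** Reconcile 9.2.5, 9.3.3, 9.5.4 and the reference in 6.4.2 into one cardiac retreatment statement, placed in one section and cross-referenced from the others. It should state:

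- how symptomatic myocarditis is handled, and how asymptomatic myocarditis and isolated enzyme rises relate to it;
- how each grade of ischemia is handled;
- whether a stop applies to IL-2 only or to both agents;
- which section governs where the optional guidance in 9.3 and the criteria in 9.2 or 9.5 differ.

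The clinical team decides the content of each item, including which section governs. The cost is wording in a clarifying amendment; reconciling the text does not itself require new procedures, data items or sample size.

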## **9.4 Management of Grade 4 Toxicity**

Patients with Grade 4 (Life Threatening) toxicity (with the exception of those Grade 4 toxicities listed in Section 10.5) may be treated with dexamethasone 4 mg qid until side effects improve to an acceptable level as indicated. Two dose reductions of hydroxychloroquine (Levels -1 and -2 in **Table 5**) may be allowed in a patient if treatment-limiting toxicity considered 'likely' attributable to the combination (and not to IL-2 alone) by the treating investigator is observed. A pill diary will be provided and is required.

## **9.5 Toxicity Criteria for Discontinuing Treatment**

Patients will not be considered for further therapy if the following toxicities are encountered:

**9.5.1** Pulmonary toxicity requiring endotracheal intubation

**9.5.2** Renal dysfunction requiring dialysis

**9.5.3** Grade 4 cardiac dysrhythmia or Grade 2 or 3 dysrhythmia not easily controlled with medical management.

**9.5.4** Myocardial ischemia (Grade 3 or 4) or infarction or symptomatic myocarditis (note:

asymptomatic CPK or CPK-MB band elevations without EKG changes are not a contraindication to further treatment).

- 9.5.5** Coma
- 9.5.6** Life-threatening sepsis
- 9.5.7** Pericardial tamponade
- 9.5.8** Bowel ischemia or perforation
- 9.5.9** Grade 4 hypertension or reversible posterior leukoencephalopathy syndrome (RPLS)
- 9.5.10** Grade > 2 pulmonary or CNS hemorrhage
- 9.5.11** Grade 4 hypertension or hemorrhage, symptomatic grade 4 venous thromboembolic event, nephrotic syndrome
- 9.5.12** Any grade arterial thromboembolic event
- 9.5.13** Grade 4 congestive heart failure
- 9.5.14** Wound dehiscence requiring medical or surgical intervention
- 9.5.15** Inability of subject to comply with study requirements
- 9.5.16** Any other severe or life-threatening toxicity which, in the opinion of the investigator, would preclude further treatment with these agents, or has not resolved substantially to an acceptable level as determined by the local PI.

Patients who have an ongoing Grade 4 or serious adverse event at the time of discontinuation from study treatment will continue to be followed until resolution of the event or until the event is considered irreversible (see Section 7.1.3).

## **10.0 DETAILED RESPONSE ASSESSMENT (also see 6.4)**

Response will be defined by NCI's Response Evaluation Criteria in Solid Tumors (RECIST) 1.1.

### **10.1 Disease Evaluation**

Measurable disease - the presence of at least one measurable lesion. If the measurable disease is restricted to a solitary lesion, its neoplastic nature should be confirmed by cytology/histology.

Measurable lesions - lesions that can be accurately measured in at least one dimension with longest diameter (longest diameter to be recorded) as  $\geq 20$  mm using conventional techniques or  $\geq 10$  mm with CT scan or  $\geq 10$  mm with calipers by clinical exam.

Malignant lymph nodes - to be considered pathologically enlarged and measurable, a lymph node must be  $\geq 15$  mm in short axis when assessed by CT scan (CT scan slice thickness recommended to be no greater than 5 mm). At baseline and in follow-up, only the short axis will be measured and followed.

Non-measurable lesions - all other lesions, including small lesions (longest diameter  $< 10$  mm or pathological lymph nodes with  $\geq 10$  to  $< 15$  mm short axis), i.e., bone lesions, leptomeningeal disease, ascites, pleural/pericardial effusion, inflammatory breast disease, lymphangitis cutis/pulmonis, cystic lesions, and also abdominal masses that are not confirmed and followed by imaging techniques. Non-measurable also includes lesions that are  $< 20$  mm by chest x-ray

Clinical lesions will only be considered measurable when they are superficial (e.g., skin nodules and palpable lymph nodes).

All measurements will be taken and recorded in metric notation, using a ruler or calipers. All baseline evaluations should be performed as closely as possible to the beginning of treatment. The same method of assessment and the same technique should be used to characterize each identified and reported lesion at baseline and during follow-up.

